6.6. Exposure to Study Drug

A data listing will be created giving the date and time of dose administration for each subject in the Safety Analysis Set.

6.7. Protocol Deviations

Protocol deviations will be identified and recorded by the site and tracked separately from the clinical database. Clinical team members on the Ironwood Study Execution Team (SET) will determine which protocol deviations are important protocol deviations (IPDs) and will categorize IPDs based on a blinded review of all protocol deviations prior to database lock and unblinding. The SET members reviewing the protocol deviations will include the study clinical operations lead, the medical director, the study biostatistician, and other personnel as appropriate.

The number and percentage of subjects with IPDs will be presented by treatment group and IPD category for the Safety Analysis Set. Protocol deviations and IPDs will be provided by subject in a data listing for the Safety Analysis Set.

A separate listing of all inclusion/exclusion criteria deviations will be provided for all randomized subjects (ie, the ITT Set).

7. SAFETY ANALYSIS

All safety parameters will be summarized using descriptive statistics. Safety analyses will be performed on the Safety Analysis Set. The safety parameters will include AEs, clinical laboratory evaluations, vital signs, and ECGs. For each laboratory parameters and ECG site interpretation, the last nonmissing assessment before the first dose of study drug will be used as the baseline for all analyses of that laboratory parameter or ECG interpretation. For numeric ECG measurements, the average of the last triplicate ECG before dosing will be used as baseline. For vital signs, the last supine measurement before dosing will be used as baseline.

All safety analyses will be performed according to the treatment actually received regardless of the allocated treatment.

7.1. Adverse Events

AEs will be coded by SOC and PT using MedDRA Version 24.0. The study investigator will assess the severity of the AE and assign a grade using the Common Terminology Criteria for Adverse Events (CTCAE). An AE is considered a treatment-emergent AE (TEAE), if the AE started after initial study drug administration and within 1 day of the last dose of study drug. In addition, an AE that started before initial study drug but worsened after the first dosing of the study drug is also considered a TEAE.

The number and percentage of subjects reporting TEAEs in each treatment group will be tabulated:

- by SOC and PT
- by SOC, PT, and CTCAE grade
- by SOC, PT, and relationship to study drug.

If a subject has more than 1 TEAE coded to the same PT, the subject will be counted only once for that PT by identifying the TEAE with the highest CTCAE grade and the closest relationship to study drug.

The incidence of the following TEAEs will be summarized by PT:

- Treatment-emergent Serious Adverse Events (TESAEs)

All AE summary tables will be sorted alphabetically by SOC and each PT within the SOC will be sorted by decreasing frequency for the IW-3300 group.

A TEAE summary table with all the non-SAEs by SOC and PT will be generated to support the clinicaltrials.gov reporting requirements.

AE listings will be presented for all subjects with AEs, all screened subjects with SAEs, all SAEs (regardless of treatment-emergent status), and subjects who died (if any), respectively.

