1.3. Schedule of Activities

Table 1: Schedule of Activities

Study Procedure ↓	Study Period →	Screening Period			Clinic Period		Follow-up Period
		Visit/Day →	Screening Visit Day -28 to Day -8	Check-in Day -1	Dosing Day 1	Discharge Day 2 ^a	
Informed consent		X					
Eligibility criteria		X	X	X			
Medical history		X					
Demographics		X					
Body weight & height ^b		X	X	X		X	
Urine drug & alcohol screen		X	X				
Urine cotinine test		X					
Physical examination ^c		X	X	X		X	
Vital signs ^d		X			Pre: 0 ($\leq 25m$) Post: 0.5, 1, 2, 4, 6, and 8h ($\pm 10m$)	24h post-Day 1 dose ($\pm 25m$)	
Triplete 12-lead ECG ^e		X	X	X	Pre 1h ($\pm 30m$) Post: 2h ($\pm 30m$)	X ^f	
Clinical chemistry, hematology, urinalysis		X	X	X	Pre: 0 ($\leq 15m$) Post: 6h ($\pm 30m$)	24h post-Day 1 dose ($\pm 15m$)	
ESR and CRP				X		24h post-Day 1 dose ($\pm 15m$)	

Study Procedure ↓	Study Period →	Screening Period	Clinic Period			Follow-up Period
			Screening Visit Day -28 to Day -8	Check-in Day -1	Dosing Day 1	
SARS-CoV-2 testing		X	X			
HIV & hepatitis panel		X				
BBMD training		X				
BBMD dispensed		X	X			
Daily BBMD completion ^g			Day -8 through Day -2	X	X	X
BBMD collection and review ^h				X		X
Concomitant medications		X	X	X	X	X
AE monitoring		X	X	X	X	X
Subject confinement to clinic ⁱ			X	X	X	
Start of predose fast ^j					Pre: ≥6h	
Randomization				X		
Study drug administration ^k				X		
PK blood draws ^l					Pre: 0 (\leq 15m) Post: 0.5 (\pm 2m), 1h (\pm 10m), 2, 4, 6, and 8h (\pm 5m)	24h post-Day 1 dose (\pm 15m)
Stool collection ^m				X		Post: 0h to Discharge
Hemoccult testing						Post: 0h to Discharge

Study Period →		Screening Period		Clinic Period		Follow-up Period	
Study Procedure ↓	Visit/Day →	Screening Visit Day -28 to Day -8	Check-in Day -1	Dosing Day 1	Discharge Day 2 ^a	Follow-up Phone Call Day 14 (+3 days)	X
Follow-up phone call ^b							X

AE=adverse event; BBMD=bladder and bowel movement diary; CRP=C-reactive protein; CRU=clinical research unit; ECG=electrocardiogram; ESR=erythrocyte sedimentation rate; HIV=human immunodeficiency virus; PK=pharmacokinetic; Post=postdose; Pre=predose; SARS-CoV-2=severe acute respiratory syndrome coronavirus 2

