4.1.1.2. Clinic Period

The Clinic Period will begin at Check-in to the Phase 1 CRU on Day -1 (the day before dosing), and will end at the time of Discharge on Day 2 (the day after dosing). Following confirmation of eligibility at Check-in, subjects will be admitted to the CRU and will undergo baseline procedures. On the morning of Day 1 (note that there is no Day 0), subjects in each cohort will undergo predose assessments and will be randomized in a 3:1 ratio to receive IW-3300 or matching placebo after a fast of at least 6 hours. In Cohort 1 only, the first 2 subjects will be randomized in a 1:1 ratio to IW-3300 or placebo and dosed at least 4 hours before the remaining subjects in the cohort.

Blood and stool samples for PK assessments will be collected at specified times predose (blood) and postdose (blood and stool) during the Clinic Period (see SoA in [Table 1](#)). Throughout the Clinic Period, safety assessments will be performed and subjects will continue to enter their BM information into the BBMD on an event-driven basis. Bladder and urination information in the BBMD will be collected on Day 1 predose and Day 2, with a 24-hour recall period at each timepoint. Subjects will be confined to the CRU from Check-in (Day -1) through 1 day of dosing until Discharge (Day 2), which will occur after completion of the assessments (at least 24 hours after administration of study drug) and at the investigator's discretion.

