9.4.2. Primary Endpoints Analyses

The primary endpoint analysis will be based on the Safety Analysis Set.

AE verbatim terms will be coded in the electronic data capture (EDC) system against the most current version of the Medical Dictionary for Regulatory Activities (MedDRA) available at the start of the study.

TEAEs are defined in Section 10.3.1. The TEAEs and TESAEs for 1 calendar day postdose will be summarized by system organ class, preferred term, and treatment (or cohort).

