10.3.1.2. TEAE Definition

- A TEAE is an event that emerges, or a pre-existing event that worsens, any time after the initiation of the first dosing of the investigational product.

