12.1.4. Missing Date of Adverse Events

For AEs with partial start dates, nonmissing date elements, such as start year, will be used to determine if the AE is treatment-emergent or not. If a determination cannot be made using the nonmissing date elements as to when the AE occurred relative to study drug administration (eg, AE start day is missing and the year and month are the same as the year and month of the first dose of study drug), then the AE will be classified as treatment-emergent.

To facilitate categorization of AEs as treatment-emergent, the start date will be imputed. The stop date will be imputed if it is needed to determine whether an AE is treatment emergent.

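### SAP 7.1 puts a 1-day onset limit into the TEAE definition for new events only, so its rule departs from protocol 10.3.1.2 on late new events and from protocol 9.4.2 on late worsened events

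*SAP*

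**What the plan says.** Three current passages decide which events enter the primary tables.

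- Protocol 10.3.1.2 defines a TEAE as an event that emerges, or a pre-existing one that worsens, "any time after the initiation of the first dosing of the investigational product". Neither type has an upper time limit.
- Protocol 9.4.2 refers to Section 10.3.1 for the definition and then sets the period reported: "The TEAEs and TESAEs for 1 calendar day postdose will be summarized". It draws no line between new and worsened events.
- SAP 7.1 makes the time limit part of the definition. A new AE is treatment-emergent "if the AE started after initial study drug administration and within 1 day of the last dose of study drug". For the other type, "an AE that started before initial study drug but worsened after the first dosing of the study drug is also considered a TEAE", with no time limit given.

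Protocol 8.3.1 has AEs and SAEs collected from consent to the Follow-up Phone Call or early termination; protocol 4.1.1.3 places the call at Day 14 (+3). The SAP 7.1 listings cover all subjects with AEs and "all SAEs (regardless of treatment-emergent status"). The incidence tables in that section, including the registry table of non-serious events, are restricted to TEAEs. The SAP does not mention or explain a departure from the protocol definition.

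**The concern.** Protocol 9.4 presents the SAP as a fuller technical account of the protocol's analyses, so the two should select the same events for the only primary endpoints. They do not. As the SAP is written, a pretreatment AE that worsens on Day 5 enters the incidence tables, although protocol 9.4.2 would leave it out. A new AE that starts on Day 5 does not enter them, although protocol 10.3.1.2 calls it a TEAE. Whether a late event is counted thus depends on whether it is new or worsened, a distinction the protocol does not make for this purpose.

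A wider gap lies behind this. A new SAE with a known onset on Day 3 or later would be in no TESAE, grade or relationship table, and a new late non-serious AE would be missing from the registry table. Protocol 4.2 gives measuring the rate of spontaneous AEs as a reason for having a placebo group. For new events from Day 3 on, no planned table makes that comparison.

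**Working it through.** The plan gives no figure to reproduce: protocol 9.1 plans no testing and protocol 9.2 has no sample size calculation. The check applies each rule to the same event types. **Assumption:** both 1 day and 1 calendar day run to the end of Day 2.

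**Step 1. Is the event counted?**

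| Event | Protocol 10.3.1.2 (definition) | Protocol 9.4.2 (primary summary) | SAP 7.1 |
|---|---|---|---|
| New, by Day 2 | yes | yes | yes |
| New, Day 3 or later | yes | no | no |
| Worsened, by Day 2 | yes | yes | yes |
| Worsened, Day 3 or later | yes | no | yes |

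All three columns agree in 2 of 4 rows. The SAP agrees with 10.3.1.2 in 3 of 4 and with 9.4.2 in a different 3 of 4. These are counts of rule outcomes; they say nothing about how often each event type occurs.

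**Step 2. How much follow-up lies outside the limit?** Dosing is on Day 1 and the call on Day 14 to Day 17, which is 13 to 16 days after dosing. Outside the limit: (13 − 1)/13 = 92.3% to (16 − 1)/16 = 93.8%.

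**Step 3. What does one subject change?** Group sizes follow from protocol 1.1.7: 6 per dose group, and pooled placebo of 4 × 2 = 8 or 5 × 2 = 10. Take a subject whose only postdose event is late.

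- Late new event in a dose group: 1/6 under 10.3.1.2, 0/6 under 9.4.2 and 0/6 under the SAP.
- Late worsened event in a dose group: 1/6 under 10.3.1.2, 0/6 under 9.4.2 and 1/6 under the SAP.

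Exact (Clopper-Pearson) 95% intervals, where the upper limit for 0/n is 1 − 0.025^(1/n):

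| n | 0/n | 1/n |
|---|---|---|
| 6 | 0% (0 to 45.9%) | 16.7% (0.4 to 64.1%) |
| 8 | 0% (0 to 36.9%) | 12.5% (0.3 to 52.7%) |
| 10 | 0% (0 to 30.9%) | 10.0% (0.3 to 44.5%) |

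**Step 4. How likely is at least one such subject?** The documents give no rate of late events. For an assumed per-subject probability p of an event on which the rules disagree, and 40 subjects, the chance is 1 − (1 − p)^40.

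| Assumed p | Chance of at least one |
|---|---|
| 0.5% | 18% |
| 1% | 33% |
| 2% | 55% |
| 5% | 87% |
| 10% | 98.5% |

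**The case against.** Much of the case on the other side is sound, and it rules out several stronger readings that a reader might infer.

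- **Three rival definitions.** The protocol does not contradict itself. Section 9.4.2 takes the 10.3.1 definition by cross-reference and adds a reporting window. The conflict lies between the SAP and each of these two parts.
- **SAP counts that must be wrong.** The rules differ, but the counts differ only if late events occur in subjects not already counted. If there are none, all three agree.
- **The SAP alone removes late SAEs from the tables.** Protocol 9.4.2 leaves late new events out of the primary summary too. The 0/6 versus 1/6 contrast for a late new event therefore measures the protocol's own window. Only the late worsened case sets the SAP against 9.4.2.
- **A strict 24-hour limit that drops findings at Discharge.** Discharge is an event "which will occur after completion of the assessments (at least 24 hours after administration of study drug"), and the vital signs at "24h post-Day 1 dose" may be taken 25 minutes late, at about 24.4 hours. But the SAP's other timing rules work by date (6.5, 12.1.3, 12.1.4), so through Day 2 is the natural reading. SAP 7.1 also goes by when an AE started, whereas the 24.4 hours is when a measurement is taken.
- **A serious flaw in the partial-date rule.** Under SAP 12.1.4, if timing relative to dosing cannot be determined, "then the AE will be classified as treatment-emergent". A late AE with no start day in the dosing month would thus be counted, while the same AE with a known Day 5 onset would not. This is a conservative convention with a small gap.

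The late worsened case is also narrow. Subjects are healthy. Under protocol 8.3.1, a condition present at screening becomes an AE only if it deteriorates, and its start may then be taken as the date of deterioration. The unlimited limb would then reach mainly AEs that began between consent and dosing.

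Finally, with 6 active subjects per cohort, the listings show every late event, and protocol 9.4.5 adds listings of severe and drug-related AEs. That stands, but a listing does not give incidence by group, and incidence is the endpoint.

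**Conclusion.** The inconsistency holds on the current text and should be corrected, though it does not threaten the trial. SAP 7.1 does not reproduce the protocol's definition, because it drops late new events. Nor does it reproduce the protocol's summary window, because it keeps late worsened events. Separately, no planned incidence table covers new events after about Day 2. The protocol and the SAP share responsibility for that.

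The size is at most one step in a small count for each affected subject: 16.7 percentage points in a dose group, and 12.5 or 10.0 in pooled placebo. This assumes that the late event is the subject's only one and that both time limits run to the end of Day 2. How many such subjects to expect cannot be learned from the documents.

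Four features limit the impact. Late events are still listed, no hypothesis is tested, escalation uses blinded data through Discharge on Day 2 (protocol 6.6), and the same rule applies to IW-3300 and placebo.

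**What to change.** Before database lock and unblinding:

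1. In SAP 7.1, restore the protocol 10.3.1.2 definition without a time limit.
2. Apply the protocol 9.4.2 limit as a summary window in one stated unit: calendar day, with onset or worsening through Day 2. Apply it equally to new and worsened events.
3. Beside the 1-day summary, add TEAE and TESAE incidence tables from dosing to the Follow-up Phone Call or early termination. They should cover SOC and PT, CTCAE grade, relationship, and the registry table of non-serious events.
4. As a minor clarification, state in SAP 12.1.4 how partial dates are handled for the window.

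Protocol 9.4.2 can stay as it is, with the 1-day table as the prespecified summary. The cost is some SAP wording and a few extra tables, with no new data and no change to conduct. The drawback is that the added tables will count some unrelated late events; the placebo group and the relationship table help in reading them.

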7.2. Clinical Laboratory Data

Descriptive statistics for clinical laboratory values (in SI units) and changes from baseline at each postbaseline time point will be presented by treatment group for each clinical laboratory parameter. All laboratory data will be listed for the Safety Analysis Set.

Table 1: Laboratory Assessments

Laboratory Assessments	Parameters			
Hematology	Platelet count	RBC Indices: MCV MCH MCHC % Reticulocytes		WBC Count with Differential: Neutrophils Lymphocytes Monocytes Eosinophils Basophils
	RBC count			
	Hemoglobin			
	Hematocrit			
Clinical Chemistry	Blood urea nitrogen (BUN)	Potassium	AST	Total and direct bilirubin
	Creatinine	Sodium	ALT	Total protein
	Glucose	Calcium	Alkaline phosphatase	Magnesium
	Chloride	Albumin	Bicarbonate	Phosphate
	Cholesterol	Uric acid		
Routine Urinalysis	
 Specific gravity pH, glucose, protein, blood, and ketones, by dipstick Microscopic examination (if blood or protein is abnormal) Urine culture (if urinary tract infection is suspected) 			
Inflammatory markers	
 ESR (analyzed at an outside laboratory) CRP 			
Hemoccult testing	
 Point-of-care hemoccult test 			
Other Screening Tests	
 Alcohol and drug screen (to include at minimum: amphetamines, barbiturates, cocaine, opiates, cannabinoids, and benzodiazepines). Urine cotinine test SARS-CoV-2 testing (Screening and Check-in) HIV antibody and hepatitis panel (HBsAg, and HCV antibody). 			

For each clinical laboratory parameter, the number and percentage of subjects with potentially clinically significant (PCS) postbaseline clinical laboratory values will be tabulated by treatment group. The criteria for PCS laboratory values are described in [Table 2](#). The percentages will be calculated relative to the number of subjects with non-PCS baseline values and at least 1 postbaseline assessment. The numerator will be the total number of subjects who had non-PCS values at baseline and who had at least 1 postbaseline PCS value.

A supportive listing for subjects with PCS postbaseline values will be provided and will include the subject ID number, all lab values, both pre- and postbaseline, and a flag marking the PCS laboratory values.

Table 2: Criteria for Potentially Clinically Significant Laboratory Tests

Parameter	SI Unit	Lower Limit	Higher Limit
Chemistry			
Albumin	g/L	$<0.9 \times \text{LLN}$	$>1.1 \times \text{ULN}$
Alanine aminotransferase	U/L	—	$\geq 3 \times \text{ULN}$
Alkaline phosphatase	U/L	—	$\geq 3 \times \text{ULN}$
Aspartate aminotransferase	U/L	—	$\geq 3 \times \text{ULN}$
Bicarbonate	mmol/L	$<0.9 \times \text{LLN}$	$>1.1 \times \text{ULN}$
Bilirubin, total	$\mu\text{mol/L}$	—	$>1.5 \times \text{ULN}$
Calcium	mmol/L	$<0.9 \times \text{LLN}$	$>1.1 \times \text{ULN}$
Chloride	mmol/L	$<0.9 \times \text{LLN}$	$>1.1 \times \text{ULN}$
Cholesterol, total	mmol/L	—	$>1.6 \times \text{ULN}$
Creatinine	$\mu\text{mol/L}$	—	$>1.3 \times \text{ULN}$
Glucose	mmol/L	$<0.8 \times \text{LLN}$	$>1.4 \times \text{ULN}$
Magnesium	mmol/L	$<0.9 \times \text{LLN}$	$>1.1 \times \text{ULN}$
Phosphate	mmol/L	$<0.9 \times \text{LLN}$	$>1.1 \times \text{ULN}$
Potassium	mmol/L	$<0.9 \times \text{LLN}$	$>1.1 \times \text{ULN}$
Protein, total	g/L	$<0.9 \times \text{LLN}$	$>1.1 \times \text{ULN}$
Sodium	mmol/L	$<0.9 \times \text{LLN}$	$>1.1 \times \text{ULN}$
Urea nitrogen	mmol/L	—	$>1.2 \times \text{ULN}$
Uric acid	$\mu\text{mol/L}$	$<0.9 \times \text{LLN}$	$>1.1 \times \text{ULN}$
Hematology			
Basophils, absolute cell count	$10^9/\text{L}$	—	$>3 \times \text{ULN}$
Eosinophils, absolute cell count	$10^9/\text{L}$	—	$>3 \times \text{ULN}$
Hematocrit	Ratio	$<0.9 \times \text{LLN}$	$>1.1 \times \text{ULN}$
Hemoglobin	g/L	$<0.9 \times \text{LLN}$	$>1.1 \times \text{ULN}$
Lymphocytes, absolute cell count	$10^9/\text{L}$	$<0.8 \times \text{LLN}$	$>1.5 \times \text{ULN}$
Mean corpuscular hemoglobin	Pg	—	$>3 \times \text{ULN}$
Mean corpuscular hemoglobin concentration	g/L	—	$>3 \times \text{ULN}$
Mean corpuscular volume	fL	$<0.9 \times \text{LLN}$	$>1.1 \times \text{ULN}$
Monocytes, absolute cell count	$10^9/\text{L}$	—	$>3 \times \text{ULN}$
Neutrophils, absolute cell count	$10^9/\text{L}$	$<0.8 \times \text{LLN}$	$>1.5 \times \text{ULN}$
Platelet count	$10^9/\text{L}$	$<0.5 \times \text{LLN}$	$>1.5 \times \text{ULN}$

Parameter	SI Unit	Lower Limit	Higher Limit
Red blood cell count	$10^{12}/L$	$<0.9 \times LLN$	$>1.1 \times ULN$
White blood cell count	$10^9/L$	$<0.7 \times LLN$	$>1.5 \times ULN$

LLN: Lower limit of normal value provided by the laboratory

ULN: Upper limit of normal value provided by the laboratory

7.3. Vital Signs

Descriptive statistics for body weight and vital signs (ie, oral temperature, supine systolic and diastolic blood pressure, and pulse) and changes from baseline values at each time point will be presented by treatment group, and all the data will be listed. If there are multiple measurements for the same time point, the first one will be used for the by-time point analysis.

The number and percentage of subjects with PCS postbaseline vital signs will be tabulated by treatment group. A vital sign value will be considered PCS if it meets both the observed value criterion and the change from baseline criterion. The criteria for PCS vital sign values are detailed in [Table 3](#). The PCS percentages will be calculated relative to the number of subjects with baseline values and at least 1 assessment in the corresponding postbaseline period. The numerator will be the total number of subjects with available baseline values and at least 1 postbaseline PCS value.

A supportive data listing for subjects with PCS postbaseline values will be provided, including the subject ID number, baseline and postbaseline values for each visit, and a flag indicating the PCS vital sign values.

Table 3: Criteria for Potentially Clinically Significant Vital Signs

Vital Sign Parameter	Flag	Criteria ^a	
		Observed Value	Change from Baseline
Supine systolic blood pressure (mmHg)	High	≥180	Increase of ≥20
	Low	≤90	Decrease of ≥20
Supine diastolic blood pressure (mmHg)	High	≥105	Increase of ≥15
	Low	≤50	Decrease of ≥15
Supine pulse (beats per minute)	High	≥120	Increase of ≥15
	Low	≤50	Decrease of ≥15
Weight (kg)	High	-	Increase of ≥7%
	Low	-	Decrease of ≥7%

^a A postbaseline value is considered as a PCS value if it meets the criteria for both observed value and change from baseline.

In addition to supine measurements, at the predose measurement and at postdose time points 1, 6, and 24 hours, standing blood pressure and pulse will be measured 3 minutes after the supine measurements are taken. The standing blood pressure will be used to assess indicators of orthostatic hypotension. The criteria for testing positive for the orthostatic hypotension indicators are presented in [Table 4](#).

Table 4: Criteria for Orthostatic Hypotension Indicators

Blood Pressure Parameter	Change from Baseline
Supine systolic blood pressure (mmHg)	Increase of ≥20 mmHg
Supine diastolic blood pressure (mmHg)	Increase of ≥10 mmHg

Subjects meeting either one of these two criteria are considered to be positive for indicators of orthostatic hypotension. The number and percent of subjects who are positive for these indicators will be tabulated by treatment group and by period (baseline versus postbaseline).

7.4. **Electrocardiogram**

TriPLICATE 12-lead ECGs will be obtained as outlined in the Schedule of Activities. An average of the 3 consecutive ECG values for each parameter (heart rate, PR interval, QRS interval, QT interval, and QTc interval), or 1 or 2 values if all 3 are not available, will be used for generating the summary statistics. Descriptive statistics for ECG parameters and their changes from baseline at each assessment time point will be presented by treatment group. QTc interval will be calculated using Fridericia correction ($QTcF=QT/(RR)^{1/3}$); if RR is not available, it will be replaced with 60/hr in the correction formula. ECG interpretation (designated as normal, abnormal not clinically significant, abnormal clinically significant) will be summarized by time point. A shift table from baseline to each visit for qualitative ECG results will be presented and all the data will be listed.

In addition, the number and percentage of subjects with PCS postbaseline ECG results will be tabulated by treatment group. An ECG value will be considered PCS if it meets the observed value criterion. The criteria for PCS ECG values are detailed in [Table 5](#). The percentages will be calculated relative to the number of subjects with available non-PCS baseline values and at least 1 postbaseline assessment. The potential numerator will be the total number of subjects with available non-PCS baseline values and at least 1 postbaseline PCS value in the corresponding postbaseline period.

A supportive data listing for subjects with PCS postbaseline values will be provided, including the subject ID number, baseline and postbaseline values for each visit, and a flag indicating the PCS ECG values.

Table 5: Criteria for Potentially Clinically Significant ECG Values

ECG Parameter	Unit	Higher Limit
QRS Interval	msec	≥ 150
PR Interval	msec	≥ 250
QTc Interval	msec	> 500

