2.3.1. Risk Assessment

Potential Risk of Clinical Significance	Summary of Data/Rationale for Risk	Mitigation Strategy
Study Intervention: IW-3300		
Potential for diarrhea and secondary dehydration	These are class effects of GC-C agonism or effects observed in nonclinical safety pharmacology and toxicology studies of IW-3300.	Intrarectal administration will likely decrease the risk of diarrhea and subsequent dehydration. The study design includes dose escalation to closely monitor subject safety and tolerability at each dose level before dosing with a higher dose; a Dose Escalation Committee will conduct blinded reviews of all the safety parameters of the dosing cohort through Discharge (Day 2) in order to make decisions regarding escalation to the next dose. Orthostatic vital sign measurements will be taken to evaluate the potential for volume depletion. The daily BM frequency and stool consistency will be monitored in real time to evaluate changes in bowel habits and the potential risk of diarrhea. Stopping rules will also be in place to evaluate continued dosing (Section 7.1.1); dosing within a cohort may be temporarily suspended in the event of a diarrhea or dehydration serious adverse event (SAE); ≥ 1 subject with Grade 3 diarrhea (increase from baseline of >7 stools per day and/or watery stools [BSFS score of 7] resulting in a limiting of self-care activities) or dehydration (hospitalization indicated); or ≥ 2 subjects with Grade 2 diarrhea (increase from baseline of 4 to 6 stools per day and/or watery stools [BSFS score of 7] resulting in a limiting of instrumental activities) or dehydration (intravenous fluids indicated).

Potential Risk of Clinical Significance	Summary of Data/Rationale for Risk	Mitigation Strategy

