5.1.3. Weight

6. Body mass index (BMI) within the range 18.5 to 35.0 kg/m² (inclusive) at the Screening Visit.

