^a Subjects will be discharged on Day 2 unless they have physical examination findings or laboratory abnormalities that are considered by the investigator to be clinically meaningful. In the event that a subject discontinues from the study, an early termination visit will be performed prior to discharge from the CRU. The early termination assessments will be the same as those conducted at Discharge (Day 2). Every effort should be made and documented to ensure that safety procedures scheduled for Discharge are performed at the early termination visit.

^b Height will only be measured at the Screening Visit. At Check-in (Day -1) and Discharge (Day 2), subjects will be weighed in the morning upon awakening and before they ingest any water or food.

^c Rectal examination should be performed at each physical examination; the rectal examination at all timepoints should include a digital rectal examination and inspection of the perianal area for redness or irritation.

^d Vital signs will include oral temperature, blood pressure, and pulse rate. Side-lying blood pressure and pulse will be obtained at the 0.5 hour postdose timepoint on Day 1 (consistent with the position required following dosing). Blood pressure and pulse at the 2, 4, and 8 hour postdose timepoints should be preceded by at least 5 minutes of rest for the subject in a quiet setting without distractions (eg, television, cell phones). At all other timepoints (ie, predose and 1, 6, and 24 hours postdose), orthostatic blood pressure and pulse measurements will be obtained; subject must lie quietly for ≥5 minutes before supine/semisupine blood pressure and pulse measurements are taken, then assume standing position for 3 minutes before standing blood pressure and pulse measurements are taken. If a subject has orthostatic symptoms upon standing (eg, palpitation, dizziness), they will be assisted and asked to lie down without waiting the 3 minutes for vital sign assessment. Orthostatic measurements may be taken at other vital signs collection timepoints if clinically indicated, at the discretion of the investigator. When applicable, vital sign measurements will be obtained immediately before blood draws.

^e ECGs should be obtained after the subject has been supine for at least 5 minutes. At each timepoint required, 3 individual ECG tracings should be obtained as closely as possible in succession, but no more than 2 minutes apart. The full set of triplicates should be completed in less than 4 minutes.

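### The SAP's PCS limits for MCH and MCHC cannot be met, and those for weight, sodium and (less strongly) chloride are too wide to show mild or moderate fluid loss after one dose

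*SAP*

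**What the plan says.** - **Risk.** The first risk listed in Protocol 2.3.1 is "Potential for diarrhea and secondary dehydration".
- **Laboratory flags.** In SAP 7.2, "The criteria for PCS laboratory values are described in" Table 2, and a count and percentage of flagged subjects is planned for each laboratory parameter by treatment group. Sodium and chloride are flagged below 0.9×LLN or above 1.1×ULN. MCH and "Mean corpuscular hemoglobin concentration" have no lower limit and are flagged only above 3×ULN. MCV, the third red-cell index in the table, has 0.9×LLN / 1.1×ULN.
- **Weight flag.** SAP 7.3 states: "A vital sign value will be considered PCS if it meets both the observed value criterion and the change from baseline criterion". In Table 3 the observed-value cell for weight is a dash, so the change alone decides. The low row is "Decrease of ≥7" percent.
- **Timing.** Footnote b of the schedule (SAP 12.3) reads: "At Check-in (Day -1) and Discharge (Day 2), subjects will be weighed in the morning upon awakening". Protocol 4.1.1.2 adds "note that there is no Day 0", so these two weighings are two calendar days apart and the second is about 24 h after the single dose. Postdose chemistry is drawn at 6 h and 24 h.
- **Reference limits.** Table 2 takes LLN and ULN from the laboratory. The documents give no values.

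**The concern.** A PCS flag is useful if an affected subject could plausibly trip it and most unaffected subjects would not. Two separate problems appear here.

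First, three times the upper limit suits a cell count that can multiply. It does not suit a red-cell index that varies within a narrow band. In Table 2 the pattern of no lower limit with >3×ULN otherwise occurs only for basophils, eosinophils and monocytes, which suggests that MCH and MCHC were given the wrong rule.

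Second, a 7% weight change is not scaled to fluid loss over roughly a day, and a 10% margin is very wide for electrolytes with narrow reference ranges. The tables would then probably show zero flagged subjects for weight and sodium at every dose, even if the drug caused a moderate loss of fluid. A reader of the study report could take those zeros as evidence on the first-listed risk, when the limits almost guarantee them.

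**Working it through.** The plan gives no figure of its own to reproduce: it does not derive these limits, and it has no sample-size calculation. The check puts numbers into the stated multipliers. Reference ranges, heights, stool volumes and body-water fraction are assumptions.

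1. **MCHC and MCH.** MCHC at an assumed ULN of 350–370 g/L: 3 × 350 = 1050 and 3 × 370 = 1110 g/L, more than 1 kg of hemoglobin per liter of red cells, which is not physically possible. MCH at an assumed ULN of 32–35 pg: 3 × 32 = 96 and 3 × 35 = 105 pg. Since MCH (pg) = MCHC (g/L) × MCV (fL) / 1000, even with MCHC at its upper limit this needs a mean cell volume of 96/0.370 = 259 fL to 105/0.350 = 300 fL. Neither row can be met.

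2. **Weight in kilograms.** Loss needed = 0.07 × weight: 3.5 kg at 50 kg, 4.9 kg at 70 kg, 7.0 kg at 100 kg. Protocol 5.1.3 sets "Body mass index (BMI) within the range 18.5 to 35.0 kg/m² (inclusive) at the Screening Visit". At an assumed height of 1.70 m, 0.07 × BMI × 1.70² = 3.74, 5.06 and 7.08 kg for BMI 18.5, 25 and 35. Over heights of 1.55–1.85 m the span is 3.11–8.39 kg.

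3. **Weight against stool loss.** Protocol 2.3.1 describes Grade 3 diarrhea by frequency as more than 7 stools per day above baseline. Take 8 extra stools at an assumed 100–300 mL each, ignoring any fluid drunk: 8 × 0.1 to 8 × 0.3 = 0.8–2.4 L. Over 70 kg that is 1.1–3.4%. Reaching 4.9 kg would take 4.9/0.3 = 16.3 to 4.9/0.1 = 49 such stools.

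4. **Sodium.** Assumed range 135–145 mmol/L: limits 0.9 × 135 = 121.5 and 1.1 × 145 = 159.5, so 13.5/10 = 1.35 and 14.5/10 = 1.45 range-widths outside normal. Assumed 133–148: 119.7 and 162.8, or 13.3/15 = 0.89 and 14.8/15 = 0.99. Pure water loss to raise sodium from 140 to the high limit is TBW × (1 − 140/limit). With TBW = 0.6 × 70 = 42 L and a limit of 159.5, this is 42 × 0.122 = 5.13 L, or 7.3% of body weight. For ULN 144–148 it is 4.88–5.88 L (7.0–8.4%).

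5. **Potassium, for contrast.** Assumed 3.5–5.0 mmol/L with the same multipliers: 0.35/1.5 = 0.23 and 0.50/1.5 = 0.33 range-widths.

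6. **Chloride.** Assumed 98–107 mmol/L: 9.8/9 = 1.09 and 10.7/9 = 1.19 range-widths. Assumed 96–110: 9.6/14 = 0.69 and 11.0/14 = 0.79. The point is weaker and depends on the laboratory.

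7. **Flags that stay closer to normal.** Urea nitrogen is flagged above 1.2×ULN, or 7.7–9.8 mmol/L at an assumed ULN of 6.4–8.2. Creatinine is flagged above 1.3×ULN, or 117–150 µmol/L at an assumed ULN of 90–115. Bicarbonate is flagged below 0.9×LLN, or 18.0–20.7 mmol/L at an assumed LLN of 20–23.

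8. **What a mean shows.** If one of six subjects loses 3% of 70 kg (2.1 kg), the group mean moves by 2.1/6 = 0.35 kg.

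**The case against.** A reader might infer that every dehydration flag in this trial will be empty whatever the drug does. The documents do not support that. The SAP never labels weight, sodium or chloride as the dehydration flags. The same tables flag urea nitrogen, creatinine, potassium, bicarbonate, hematocrit, low blood pressure and high pulse, several within ordinary reach. The protocol's named measure of volume depletion is orthostatic vital signs, which SAP 7.3 tabulates separately. (Table 4 prints its criteria as supine increases although the text refers to standing pressure; that is a different matter.) Severe fluid loss could also reach the weight, sodium and chloride limits. MCH and MCHC are not dehydration markers at all.

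Nor are smaller shifts hidden. Descriptive statistics include minimum and maximum (SAP 12.1.1), so the largest individual fall at each time point is reported, and all data are listed for at most 40 subjects. The main risk is also followed through graded adverse events, stool monitoring and the suspension criteria in Protocol 2.3.1 and 7.1.1.

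All of this stands, and it limits the harm. It does not rescue the rows themselves. A minimum shows one extreme but gives no count of affected subjects by dose, which is what a PCS table is for.

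One further objection has some force. Giving MCHC 0.9/1.1 still leaves wide limits: at an assumed 320–360 g/L they are 288 and 396, or 32/40 = 0.8 and 36/40 = 0.9 range-widths outside normal. That change makes the row attainable and consistent with MCV; it does not make it sensitive.

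**Conclusion.** The point holds in a limited form. The MCH and MCHC limits cannot be met, and this holds across the assumed reference limits. The weight limit needs about 4.9 kg at 70 kg, well above the 0.8–2.4 L implied by eight extra stools at the assumed volumes. The sodium limits lie about 0.9 to 1.45 range-widths outside normal across both assumed ranges. Chloride lies at 0.69 to 1.19, so the case there is weaker. Zeros in the weight, sodium and chloride rows should not be read as evidence against mild or moderate fluid loss.

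The consequence is for presentation and interpretation. No safety data are lost, and no dose-escalation rule depends on these limits. All absolute laboratory values depend on reference ranges that the documents do not give, and the stool volumes are illustrative.

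**What to change.** Amend the SAP before database lock; these are reporting flags only.

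- **Table 2, MCH and MCHC:** replace the single >3×ULN limit with 0.9×LLN / 1.1×ULN, as for MCV.
- **Sodium and chloride:** add a low/normal/high shift table against the laboratory reference range, from baseline to the worst of the 6 h and 24 h values, by dose and for pooled placebo.
- **Table 3, weight:** replace or supplement the 7% row with the number and percentage of subjects whose weight falls by at least 2% and at least 3% from the last predose weight, by dose and for pooled placebo. Name that baseline explicitly, because SAP 7 defines the vital-sign baseline in terms of supine measurements.

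At 70 kg the new weight cuts are 1.4 and 2.1 kg. Eight extra stools would reach them at 1.4/8 = 175 mL and 2.1/8 = 263 mL each, both inside the assumed volume range. A 1% cut is not proposed: 0.7 kg over two days, with fasting and encouraged bowel emptying in between, is likely to be ordinary variation.

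The cost is SAP wording and one or two simple tables. Protocol 9.4.5 sets no PCS limits, so it needs no change. The downside is that a few flags will reflect ordinary variation. Pooled placebo gives the background, but with at most 5 × 2 = 10 subjects it is a coarse comparison.
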